3.3 Subject Recruitment, Enrollment and Screening

Subjects will be recruited, enrolled and screened using the following resources:

- From the Principal Investigator or Co-Investigator clinical practices
- Referring physicians, advertisement, etc.
- Information that is to be given to potential subjects (handouts, brochures, etc.)
- Advertisements
- Screening requirements or qualifying lab values
- Evaluation and documentation of inclusion/exclusion criteria

3.4 Subject Withdrawal

A subject may be withdrawn from the study prior to that subject completing all of the study-related procedures. Some reasons include:

Criteria for Subject Withdrawal

The following are criteria for subject discontinuation from the study:

- 1. Subject withdraws study consent.

CONFIDENTIAL

This material is the property of the Mayo Clinic. Do not disclose or use except as authorized.

2. Subject is found to be ineligible for the protocol as per the Inclusion/Exclusion criteria.
3. Subject experiences disease progression.
4. Lille scores at any time are >0.45 (treatment failure). Patient will be taken off study drug, however, we will request that they complete follow-up.
5. Failure of the subject to comply with protocol requirements.
6. Exhibition of unacceptable toxicity which would make it difficult or dangerous to comply with further protocol requirements such as study visits, blood draws, etc.
7. There are changes in medical status of the subject such that the Investigator believes that subject safety will be compromised or that it would be in the best interest of the subject to stop participation in the study.
8. Death of the subject.
9. Subjects with a test consistent with pregnancy such as a positive beta-hCG.
10. Subject is lost to follow-up.
11. Any complication that requires prolongation of the hospitalization or change in treatment and in the opinion of the investigator is related to the study drug.

Procedures for Subject Withdrawal

At the time of study withdrawal, subjects, if capable, will be asked to complete all of the procedures that would normally be performed at the Day 42 assessment. Withdrawn subjects will have a 30-day follow up phone call after their last clinical assessment.

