1.9 Power Calculation

As the primary outcome is observational, we have powered this study based upon the efficacy outcome, which is defined as a biochemical signal for success if AST/ALT is reduced by at least 30% on treatment. With no treatment, approximately 15-20% of patients reach this outcome following study drug treatment. We anticipate that a minimum of 50% will achieve this outcome. Using a conservative 2-sided assessment of superiority (50% with outcome vs. 20%), we will require 22 subjects to reach 80% statistical power.

For our efficacy outcome of AST/ALT, our primary analysis will assess a binary outcome of at least 30% reduction when on treatment. We will evaluate this with a 95% confidence interval of the percentage of subjects who have at least 30% reduction in AST/ALT on treatment, using an exact binary confidence interval. As a secondary analysis, we will use

CONFIDENTIAL

This material is the property of the Mayo Clinic. Do not disclose or use except as authorized.

robust linear regression with the change in AST/ALT at follow-up as compared to baseline as the outcome variable and baseline AST/ALT as the predictor. We will pair this analysis with a Bland-Altman plot. The goal of the secondary analysis is to assess the degree to which the reduction in AST/ALT attributable to treatment changes according to the subject's baseline AST/ALT. We will use 2-sides 5% type I error rate throughout.

2 *Study Objectives*

Primary:

- Assess the safety and tolerability and find the MTD of F-652 in patients with alcoholic hepatitis as determined by:
 - a. Absence of unexpected serious adverse events and,
 - b. Absence of worsening of alcoholic hepatitis (as determined by increase in MELD score > 5) up to Day 56 following administration of first dose of study drug.

Secondary:

- Determine the pharmacokinetics (PK) and pharmacodynamics (PD) of F-652 in patients with alcoholic hepatitis.

Additional:

- Assess the efficacy signal of F-652 in patients with alcoholic hepatitis as determined by:
 - a. Clinical: improvement in clinical status
 - b. Biochemical: Improvement in liver biochemistry, MELD and Lille scores at days 7, 28, 42 and 56
 - c. Biomarkers of IL 22 activity (CRP, SAA, triglycerides)

2.1 **Trial Design:**

The following study evaluations will be performed during the course of the Screening period (Day -3 to Day 0):

- Signed informed consent

CONFIDENTIAL

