2.3 Primary Study Endpoints/Secondary Endpoints

Primary:

- Absence of unexpected serious adverse events.

Secondary:

- Pharmacokinetics (PK) and pharmacodynamics (PD) of F-652 in patients with alcoholic hepatitis.

Efficacy Signal endpoints:

- Decrease in MELD score, Lille score, triglyceride, CRP, AST, ALT and SAA1

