3.5 Data Collection and Follow-up for Withdrawn Subjects

Even though a subject has withdrawn from the study, these patients will be followed up in the hospital and to 42 days following the last administration of the study drug. Such data is important to the integrity of the final study analysis since early withdrawal could be related to the safety profile of the study drug. If a subject withdraws consent to participate in the study, for subject safety reasons, attempts should be made to obtain permission to collect follow up information whenever possible.

4 Study Drug

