6.9 Individual Stopping Rules

The following are criteria for subject discontinuation from the study:

1. Subject withdraws study consent.
2. Subject is found to be ineligible for the protocol as per the Inclusion/Exclusion criteria.
3. Subject experiences disease progression.
4. Lille scores at any time are >0.45 (treatment failure). Patient will be taken off study drug, however, we will request that they complete follow-up.
5. A subject that requires more than 2 investigation drug (F-652) dose reductions.
6. Failure of the subject to comply with protocol requirements.
7. Exhibition of unacceptable toxicity which would make it difficult or dangerous to comply with further protocol requirements such as study visits, blood draws, etc.
8. There are changes in medical status of the subject such that the Investigator believes that subject safety will be compromised or that it would be in the best interest of the subject to stop participation in the study.
9. Death of the subject.
10. Subjects with a test consistent with pregnancy such as a positive beta-hCG.
11. Subject is lost to follow-up.
12. Any complication that requires prolongation of the hospitalization or change in treatment and in the opinion of the investigator is related to the study drug.

The investigator will utilize the National Cancer Institute's CTCAE system as a guide when determining the need for an individual participant to stop the study.

7 Statistical Plan

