7.1 Statistical Methods

Primary endpoint (safety): The number and percentage of patients with SAE and increase in MELD score > 5 up to Day 56 following administration of first dose of study drug will be summarized by each dose level. Ninety-five percent confidence interval of the percentage will be calculated too.

Summary of adverse event will also be provided by each dose level.

Secondary endpoint: Pharmacokinetics (PK) and pharmacodynamics (PD) of F-652 in patients with alcoholic hepatitis at the first dose level (10ug/kg) and subsequent dose levels will be determined by the study sponsor using standard pharmacological tools. The total exposure (area under the curve), maximum serum concentration, time at maximum concentration, last measurable serum concentration, time at last measurable concentration, clearance, volume of distribution, elimination half-life, accumulation ratio and dose proportionality will be calculated.

Efficacy signal endpoint: The main efficacy end point is the reduction of AST/ALT or serum triglycerides. If patients show a reduction of AST/ALT or serum triglyceride by 30% at day 42, the drug shows efficacy in this patient. We will calculate the percentage of patients with efficacy (rate) and its 95% confidence interval for each dose level.

We will also use the proportion of patients with 30% change of AST, ALT from baseline to Day 3, Day7, Day14, Day 28, Day 42 and Day 56 as the dependent variable, dose level and baseline AST, ALT and other patients' characteristic at baseline as the covariates to evaluate the change (efficacy) or drug by dose level. A random intercept will be included for accommodating the correlation among the repeated measurement.

Other efficacy endpoints: Paired t-test or signed-rank test will be used to compare the level Lille score. Linear mixed-effect models will be used to analyze the MELD score, triglycerides, CRP, and SAA1 in a similar way to the AST/ALT.

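### Sections 3.4/6.9 and 3.5 give conflicting follow-up for withdrawn patients, so under 3.4 alone MELD and AST/ALT changes after withdrawal would go unrecorded

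*Combined protocol and SAP*

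**What the plan says.** Section 3.4 and section 6.9 (Individual Stopping Rules) open their lists in the same way: "The following are criteria for subject discontinuation from the study". Both lists include "Subject experiences disease progression", which is not defined, together with unacceptable toxicity, a change in medical status and drug-related complications. Only the item for a Lille score above 0.45 separates coming off drug from leaving the study: those patients are asked to complete follow-up.

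The procedures paragraph of 3.4 asks withdrawn patients, if they are able, to have the Day 42 procedures at the time of withdrawal. It then adds: "Withdrawn subjects will have a 30-day follow up phone call after their last clinical assessment".

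Section 3.5 says that "these patients will be followed up in the hospital and to 42 days following the last administration of the study drug". It gives the reason that early withdrawal may be related to the drug's safety profile. It does not say whether this follow-up means visits, laboratory tests or MELD.

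The outcomes affected are these:
- Section 2 (Study Objectives), primary: "Absence of worsening of alcoholic hepatitis (as determined by increase in MELD score > 5) up to Day 56 following administration of first dose".
- Section 7.1, primary safety analysis, by dose level with 95% confidence intervals: "The number and percentage of patients with SAE and increase in MELD score > 5 up to Day 56". It has no rule for patients whose MELD is missing before the end of the period.
- Section 2.3 is narrower and names only "Absence of unexpected serious adverse events" as primary.

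**The concern.** Part of the primary safety outcome is worsening of the disease, and worsening of the disease is also a listed reason for leaving the study. The patients most likely to reach a MELD rise above 5 may therefore be the ones whose laboratory follow-up ends first. A phone call cannot supply a MELD score, AST or ALT.

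Three uses of the data are exposed:
- The by-dose rate in 7.1, where an event that happens unseen after withdrawal lowers the reported figure.
- The escalation condition in 1.6, which needs every patient in a cohort to have completed 42 or 56 days of follow-up. The plan does not say how a withdrawn patient meets it.
- The Day 42 AST/ALT response in 7.1. An early withdrawal visit that uses the Day 42 procedures could be filed as if it were Day 42.

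**Working it through.** The plan states no figure for this point, so there is none to reproduce. The check sets the two follow-up rules side by side and then shows what one unseen patient does to a small cohort.

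**1. End of follow-up under each section.** Let *d* be the day of the last dose and *w* the day of withdrawal, in nominal days. If the withdrawal visit is the last clinical assessment, the 3.4 call falls on Day *w* + 30. The 3.5 follow-up ends on Day *d* + 42.

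| Last dose *d* | Withdrawn *w* | 3.4 call (*w* + 30) | 3.5 end (*d* + 42) | Call relative to 3.5 end |
|---|---|---|---|---|
| 1 | 3 | Day 33 | Day 43 | 10 days earlier |
| 7 | 7 | Day 37 | Day 49 | 12 days earlier |
| 7 | 14 | Day 44 | Day 49 | 5 days earlier |
| 7 | 28 | Day 58 | Day 49 | 9 days later |
| 14 | 14 | Day 44 | Day 56 | 12 days earlier |
| 14 | 28 | Day 58 | Day 56 | 2 days later |

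The sections differ in anchor (last assessment or last dose), in end day, and in mode (a call or unspecified follow-up). Section 6.3 also sets the adverse event period at 42 days after the last dose, so for early withdrawals the call comes before that period ends.

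**2. What is measured and what is not.** Sections 2.2 and 5.2 put MELD at every visit. The Day 42 procedures include MELD, chemistry and coagulation, so worsening already present at withdrawal is captured if the patient can attend. Under 3.4 alone nothing is measured after that. A patient withdrawn on Day 7 then has no MELD for 42 − 7 = 35 days to Day 42, or 56 − 7 = 49 days to Day 56.

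**3. Do the scheduled visits reach the 3.5 end day?**
- Day 1 dose only: 1 + 42 = Day 43, inside the Day 42 window of ±2 days.
- Last dose Day 7: 7 + 42 = Day 49. The last visit is Day 42, which is 42 − 7 = 35 days after that dose and 7 days short.
- Last dose Day 14: 14 + 42 = Day 56, which matches the Day 56 visit.

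Section 2.2 restricts the Day 56 visit to three-dose patients, so two-dose patients who stay in the study have no scheduled MELD between Day 42 and Day 56 either.

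**4. Effect of one unseen event (assumed).** Section 1.6 has three patients per dose level, expandable to six. The intervals are exact (Clopper-Pearson). With no events the upper limit is 1 − 0.025^(1/n). For 1/n the lower limit is 1 − 0.975^(1/n), and the upper limit solves (1 − p)^n + n·p·(1 − p)^(n−1) = 0.025.

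| Count | Rate | 95% CI |
|---|---|---|
| 1/3, event seen | 33.3% | 0.8 to 90.6% |
| 0/3, counted as no event | 0% | 0 to 70.8% |
| 0/2, patient dropped | 0% | 0 to 84.2% |
| 1/6, event seen | 16.7% | 0.4 to 64.1% |
| 0/6, counted as no event | 0% | 0 to 45.9% |

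Section 7.1 does not say whether such a patient would be counted as event-free or dropped, so both are shown for the cohort of three.

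**The case against.** The strongest reply is that 3.5 already supplies what is said to be missing. It is the section on follow-up of withdrawn patients, and it states both the intent and the reason. The two sections can even be read as additive: the call in 3.4 would then come 30 days after the last assessment held under 3.5. This stands in part. The loss arises only if a site applies 3.4 alone, and the first four columns of dates above rest on that reading. It does not settle the matter, because 3.5 names no visit or test and neither section refers to the other.

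Other parts of the reply also stand. Sections 2.7 and 6.1 describe stopping drug without leaving the study. The serious adverse event component is better protected: 6.3 runs to 42 days after the last dose, and 6.4 requires later, possibly related serious events to be recorded. Section 2.3 does not include MELD among the primary endpoints.

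A reader might infer more than the documents support:
- *That MELD is not measured in patients who progress.* It is measured at each visit and at withdrawal if they are able to attend.
- *That patients leave after a small MELD rise and are counted as not worsened.* Progression is undefined. If it means the section 2 criterion of a rise above 5, the event is recorded before the patient leaves. Section 7.1 has no rule for missing MELD in either direction.
- *That an escalation decision would change.* The plan does not define dose-limiting toxicity, so it is not known whether a MELD rise counts.
- *That a fixed amount of laboratory follow-up, such as 40 days, is lost relative to 3.5.* Section 3.5 does not say that it includes laboratory tests.

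**Conclusion.** The point holds in a limited form. Sections 3.4/6.9 and 3.5 disagree on how, from which date and for how long withdrawn patients are followed, and they must be reconciled. If 3.4 alone is applied, a MELD rise above 5 or an AST/ALT change after the withdrawal visit is not recorded, nor is one in a patient too ill for that visit. Such a loss can only lower the observed number of MELD events, so it can bias the by-dose safety rate toward looking safer.

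The illustration of 0/3 or 0/2 instead of 1/3 assumes exactly one unseen event. The plan gives no withdrawal frequency, so the overall bias cannot be sized. The intervals are very wide whichever count is used; what changes is whether the dose level shows an event at all.

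This should be corrected, because the remedy is cheap and uses assessments that are mostly already planned.

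**What to change.** - **One rule.** Reconcile 3.4, 6.9 and 3.5 so that stopping study drug and ending data collection are separate, and say for each listed reason which of the two applies. The criteria for stopping drug stay as they are.
- **Follow-up content.** Patients who come off drug, and who consent and are able, keep the scheduled assessments: MELD laboratory tests, AST/ALT and adverse events, including Day 56 for three-dose patients.
- **End day.** State one end day consistent with 3.5. Day 42 does not reach it for patients last dosed on Day 7.
- **Phone call.** Keep it for patients who refuse visits or for whom visits or blood draws are unsafe, so that the toxicity and best-interest items are respected.
- **Visit labelling.** Record the withdrawal visit at its actual day, not as Day 42.
- **Analysis.** In 7.1, state how patients without MELD to the end day are counted. Add a sensitivity count that scores patients who leave for progression, or die, without a later MELD as having the event.

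The cost is amendment wording, slightly more follow-up data collection (possibly a contact at about Day 49 for patients last dosed on Day 7), and perhaps a higher reported event rate.

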3.5 Data Collection and Follow-up for Withdrawn Subjects

Even though a subject has withdrawn from the study, these patients will be followed up in the hospital and to 42 days following the last administration of the study drug. Such data is important to the integrity of the final study analysis since early withdrawal could be related to the safety profile of the study drug. If a subject withdraws consent to participate in the study, for subject safety reasons, attempts should be made to obtain permission to collect follow up information whenever possible.

4 Study Drug

4.1 Description

F-652 (Recombinant human IL-22)

The drug product (DP) was manufactured by AAIPharma Services Corp, Charleston, South Carolina under Good Manufacturing Practice for pharmaceutical products (GMP).

[figure not shown]
F-652 drug substance (DS) used to manufacture the DP was produced using standard monoclonal antibody manufacturing process. The drug substance is sent from China at -77 degrees F to South Carolina. In South Carolina, it is defrosted and lyophilized into a cake. This will be then be shipped at -2 degrees F to the sites and reconstituted.

The F-652 DP in lyophilized formulation is stored at 2–8°C prior to reconstitution. F-652 is supplied lyophilized white cake in 2 mL glass vials. Each vial contains 5 mg/mL when reconstituted with 1 mL of sterile water.

4.2 Packaging, Labeling and Storage

The Generon Corporation, Ltd. or its Agent will provide labeled study medication for the clinical trial. The investigational drug is supplied as 5 mg/vial lyophilized product in 2-mL clear glass vials. A unique number is associated with each vial and is the means of drug assignment and inventory. A sample label is provided in the figure below. Please note that the label is subject to change format but the information contained therein will not change. The label has a tear off section that should be used to identify which drug was distributed to which subject and remain with the source documentation.

Sample F-652 Product Label

Study drug should be stored and maintained between 2°–8°C prior to dispensing. The product should not be frozen at any time.

4.3 Treatment Regimen

F-652 will be administered by slow intravenous infusion over approximately 100 minutes. The study medication is reconstituted as per the protocol in 100 ml of 5% dextrose in water. To monitor, as well as prevent hypersensitivity reactions, the infusion rate will be as follows:

1. 10 ml/hr for 15 minutes
2. 20 ml/hr for 15 minutes
3. 40 ml/hr for 15 minutes
4. 80 ml/hr for 15 minutes
5. 100 ml/hr until infusion complete

That is, the total infusion will be over approximately 100 minutes. Patients will be monitored for 3 hours post-infusion with blood pressure and heart rate monitoring every 30 minutes.

CONFIDENTIAL

This material is the property of the Mayo Clinic. Do not disclose or use except as authorized.

Patients will receive two separate IV infusions separated by 6-10 days (i.e. one infusion on Day 1 and a repeat infusion approximately one week later depending on outpatient scheduling). After information is received regarding the primary end point (safety) at the first dose (10ug/kg), and the 10ug/kg dose determined to be safe, the 2nd cohort of patient will be administered the 30ug/kg dose. Further escalation will follow this scheme. If evaluations demonstrate safety and efficacy signals, patients in the final dose escalation cohort will receive a third dose of the study drug at the maximum tolerated dose on Day 14.

Medications allowed: Corticosteroids, pentoxifylline, antibiotics, acamprosate, and Baclofen, as well as any other medication deemed to be essential for the treatment of the patient will be allowed.

Prohibited medications: Biological agents and any other concomitant investigational agents.

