When AEs were assessed according to dosing, subcutaneous route at a dose of 2 $\mu\text{g}/\text{kg}$ had a delayed injection site reaction (2 mild, 4 moderate) consistent of dry skin, erythema and rash whereas IV route at a dose of 30 $\mu\text{g}/\text{kg}$ was associated with dry skin (1 moderate, 2 mild), skin allergic reaction (1 moderate), eye pruritus (1 moderate), and at a dose of 45 $\mu\text{g}/\text{kg}$ with dry skin (2 mild, 5 moderate), erythema (1 moderate), eye pruritus (1 mild, 3 moderate). Review of laboratory test results, vital signs, or ECG parameters revealed no trends or changes over time following dosing with F-652 at any dose level as either subcutaneous or IV dosing.

To characterize the PK profile, single IV infusion of F-652 or placebo was administered to four cohorts of 32 healthy male volunteers at doses of 2, 10, 30 and 45 $\mu\text{g}/\text{kg}$. Both Cmax and exposure (area under the maximum plasma concentration-time curve [AUC]0-24h) of F-652 increased proportionally with increasing doses in the dose range of 2 $\mu\text{g}/\text{kg}$ to 45 $\mu\text{g}/\text{kg}$. Tmax observed was 0.7 hr for 2 $\mu\text{g}/\text{kg}$ and 0.2 hr for 10, 30, and 45 $\mu\text{g}/\text{kg}$. The t1/2 values ranged from 39.4–206 hours and also increased with increasing dose levels. No F-652 was detected in the samples collected from control subjects.

Summary of Related TEAEs for IV Infusion Adverse Event	IV (N=40) S (%) E
Dry skin	10 (25.0%)
Eye pruritus	3 (7.5%)
Rash erythematous	2 (5.0%)
Chills	1 (2.5%)
Infusion related reaction	1 (2.5%)
Headache	1 (2.5%)
Somnolence	1 (2.5%)
Dermatitis allergic	1 (2.5%)

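### The PK draws at 30 min, 1 h and 8 h are not tied to the start or end of a 97.5-minute infusion, and none is set at its end, so Tmax can be wrong and Cmax somewhat low

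*Combined protocol and SAP*

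**What the plan says.** Section 4.3 sets a stepped infusion: "F-652 will be administered by slow intravenous infusion over approximately 100 minutes". The volume is fixed there too: "The study medication is reconstituted as per the protocol in 100 ml of 5% dextrose in water". The steps are "10 ml/hr for 15 minutes", then "20 ml/hr for 15 minutes", "40 ml/hr for 15 minutes" and "80 ml/hr for 15 minutes", with the remainder given at 100 mL/h.

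The Pharmacokinetic Sampling Schedule in Section 2.2 lists a pre-dose draw and draws at 30 min (window 5 min), 1 h (window 10 min) and 8 h (window 30 min) on Days 1 and 7. Later draws follow at 72 h for Day 1 and at 24, 48, 72 and 96 h for Day 7. No time origin is given for the 30-min, 1-h and 8-h draws. A footnote counts time from dosing, but it covers only points later than 8 h and does not say whether dosing means the start or the end of the infusion. No draw is listed at the end of infusion. Vital signs, by contrast, are explicitly timed from the end of infusion (Sections 2.1 and 4.3).

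Section 7.1 lists the PK parameters to be derived as the secondary endpoint, among them "maximum serum concentration, time at maximum concentration".

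**The concern.** With an infusion of more than an hour and a half, the choice of time zero decides whether the two early draws fall before or after the peak. If the clock starts with the infusion, both are taken while drug is still running in, and nothing is drawn near the peak. If it starts when the infusion ends, both come shortly after the peak. The table permits either reading, and about six sites will apply it (Section 1.8).

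The parameters at stake are Tmax, Cmax and the shape of the early profile. Cohorts have 3 patients (Section 1.6), so one patient timed differently is a third of a cohort. Correcting this afterwards is not assured: Section 12.4 requires the dates of administration as source data, and Section 4.4 asks for records of when drug is dispensed and used, but neither names infusion start and stop times.

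**Working it through.** **Infusion length.** Inputs are the Section 4.3 rates and the 100 mL volume.

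- First four steps, 15 min each: 10 × 0.25 + 20 × 0.25 + 40 × 0.25 + 80 × 0.25 = 2.5 + 5 + 10 + 20 = 37.5 mL in 60 min.
- Remainder: 100 − 37.5 = 62.5 mL at 100 mL/h, which takes 37.5 min.
- Total: 60 + 37.5 = 97.5 min, or 1.625 h. This agrees with the plan's stated duration to within 2.5%, so the duration itself is not in question.

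**Dose delivered at the early draws, if timed from the start.**

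- 30 min: 2.5 + 5 = 7.5 mL, or 7.5%. Over the window of 25 to 35 min: 5.8% to 10.8%.
- 1 h: 37.5 mL, or 37.5%. Over the window of 50 to 70 min: 24.2% to 54.2%.
- 8 h: 480 − 97.5 = 382.5 min, so 6.4 h after the infusion has ended. This is the first post-infusion draw.

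**Concentration relative to the true peak.** The half-lives are the 39.4 h and 206 h limits reported for healthy volunteers in Section 1.4. A one-compartment model is an assumption. With k = ln 2 / t½, and step i running at rate R_i from a_i to e_i (cut off at t if the step is still running), C(t) is proportional to Σ (R_i / k) × [exp(−k(t − e_i)) − exp(−k(t − a_i))]. The peak is at 97.5 min. After that, C(t) / peak = 2^(−(t − 97.5 min) / t½).

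For example, the 8-h draw timed from the start gives 2^(−6.375/39.4) = 0.894 and 2^(−6.375/206) = 0.979.

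| Draw | Minutes from start | % of peak, t½ 39.4 h | % of peak, t½ 206 h |
|---|---|---|---|
| 30 min from start | 30 | 7.5 | 7.5 |
| 1 h from start | 60 | 37.7 | 37.5 |
| 8 h from start | 480 | 89.4 | 97.9 |
| 30 min from end | 127.5 | 99.1 | 99.8 |
| 1 h from end | 157.5 | 98.3 | 99.7 |
| 8 h from end | 577.5 | 86.9 | 97.3 |

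**What would be reported.**

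- Timed from the start: the highest draw is at 8 h. Tmax reads 8 h against a true 1.6 h, and Cmax is 100 − 97.9 = 2.1% to 100 − 89.4 = 10.6% low.
- Timed from the end: the highest draw is the 30-min one. Tmax reads 127.5 min, about 2.1 h from the start of infusion, and Cmax is 0.2% to 0.9% low.

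**Sensitivity to a faster early phase.** The documents give no figure for one, so the effective half-lives here are assumed. With 10, 5 or 2 h, the highest draw timed from the start is 64.3%, 41.3% or 40.5% of peak (at 2 h it is the 1-h draw). The 30-min draw timed from the end is 96.6%, 93.3% or 84.1%.

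**The case against.** The strongest reply is that the practical loss is small and that the end-of-infusion reading is plausible. The columns run from pre-dose to post-dose times, and vital signs are timed from the end of infusion. On that reading the existing 30-min draw already captures more than 99% of the peak at the only half-lives the documents give, and moving it gains less than 1% of Cmax. This stands for Cmax if every site reads the table that way, but nothing in the text makes them do so.

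Two points about the evidence also stand in part. The sampling table is broken in the text, so a lost header cell that names the time origin cannot be ruled out; no surviving text supplies one. Section 12.6 plans training and instruction manuals, which might settle the matter, but they are not in the documents.

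A reader might infer three stronger things, none of which the documents support.

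- That mixed timing makes cohorts non-comparable. The nominal 1-h concentration does differ about 2.6- to 2.7-fold between the readings (98.3/37.7 to 99.7/37.5), but that concentration is not a planned output. Cmax is the highest observed value, and it moves by about 2–11% at most on the documented half-lives.
- That the grid was designed for a short infusion. Section 1.4 reports "Tmax observed was 0.7 hr for 2" µg/kg and 0.2 hr at the three higher doses, but gives neither the Phase I infusion length nor its time origin.
- That escalation decisions are at risk. Section 1.6 requires PK/PD data to be available and Section 2.4 mentions PK testing, but no Cmax or Tmax threshold is set anywhere, and Section 1.6 bases escalation and the MTD on dose-limiting toxicity.

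**Conclusion.** The point holds as a cheap improvement. Two facts come straight from the text: the early draws have no stated time origin, and no draw is set at the end of a 97.5-minute infusion although Cmax and Tmax are planned outputs. Followed from the start of infusion, the grid gives a Tmax of 8 h instead of about 1.6 h. The Cmax shortfall of about 2–11% rests on a one-compartment model and on healthy-volunteer half-lives. It would be larger with a faster early phase, which the documents do not quantify. Followed from the end, the Cmax loss is under 1%. Mixed reading across sites would mainly distort Tmax and the early profile. That sites would in fact differ is a possibility the wording allows, not something the documents show.

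**What to change.** In the PK sampling table of Section 2.2:

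- Define all post-dose times from the end of infusion.
- Take the present 30-min draw at the end of infusion instead, on Days 1 and 7. The number of draws is unchanged.
- Record the actual infusion start and stop times and the actual time of each draw, and add these to the source data listed in Section 12.4.
- State in Section 7.1 that PK parameters are computed from actual and not nominal times.

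The cost is a change to the schedule wording and a few extra time fields to record. The downside is that the 30-min point is lost. Dosing and the infusion itself are untouched. If the sponsor prefers to keep the 30-min draw, stating the time origin and recording actual times would still remove the ambiguity between sites, but would leave no draw at the peak.
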